10.2 Statistical analysis plan

As this is a feasibility study, a descriptive analysis will be performed on the data. Numbers and percentages will be presented for categorical data, mean and standard deviations for normally distributed continuous data, and median and inter-

quartile ranges for skewed data. Change in the outcome measures for the secondary objectives will also be presented between the intervention and control groups.

Further, data will also be used to help determine an adequate sample size for a larger study, and also prediction of a likely duration that recruitment will be needed for this to take place. The level of statistical significance to be used is $p<0.05$.

10.3.2 Primary outcome analysis

The primary objective will be assessed using feasibility outcomes measures. This will include the number of eligible patients (pre-screening eligibility), willingness to be recruited to study (acceptability), willingness to be randomised (acceptability/concordance), study exclusion (screen failure rates), withdrawal of patients (non-concordance), compliance with the randomised treatment, study retention (retention rates), number of patients recruited over a given time (recruitment rate), and completion of outcome measures.

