3 OBJECTIVES AND OUTCOME MEASURES/ENDPOINTS

3.1 Primary objective

To determine the feasibility of a phase IV open label, controlled multi-centre randomised trial of oral ferric maltol versus standard care postoperatively for colorectal cancer patients who have been treated with preoperative intravenous iron for anaemia. Feasibility measures will include:

- Eligible patients from screening
- Study exclusion
- Acceptability of recruitment
- Study retention

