4 TRIAL DESIGN

This study will be a single centre, open labelled, randomised controlled trial comparing the effect of postoperative oral ferric maltol (intervention group) to standard care (control group), in patients with colorectal adenocarcinoma who have received pre-operative intravenous iron for anaemia. Each patient will be expected to participate for a period of 10 to 20 weeks, depending on the time between their diagnosis and the planned operation date. The participant will be recruited after the cancer MDT meeting confirming the diagnosis of colorectal adenocarcinoma and the ensuring that the patient is suitable for operative management. All study procedures will be undertaken at the time of existing hospital appointments where possible.

Recruitment will take place following the explanation of the cancer diagnosis by the clinical team. The patients will be asked by a member of the clinical or research team to state whether they consent to being approached by the research team for further information regarding the study. If they agree, a face-to-face conversation or a phone call to the patient will be arranged to discuss the research. A letter of invitation to participate in the trial (accompanied by a patient information leaflet) will then be given or posted to the patients. The patient will be given adequate time to consider participation in the study and they will be given the opportunity to ask any questions they may have. Patients who are eligible will then be invited to consent to the study.

After consenting to participate baseline data including demographics, past medical history and existing medications will be noted. Patients will be asked to complete the 3 quality of life questionnaires and they will have their blood taken including a full blood count, haematinics

(including iron, ferritin, transferrin and transferrin saturation) urea and electrolytes, liver function tests and erythropoietin. If the patients have consented to the optional sample sub-study, the patients may be asked to give other samples of faeces, urine, saliva or sweat. Following this visit the patient will receive their preoperative intravenous iron infusion as is standard care. If they are taking any existing oral iron supplementation they will be asked to stop this treatment prior to receiving their preoperative intravenous iron. Once the surgical procedure has been performed, tissue samples from the resected bowel may be obtained for analysis.

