5 TRIAL SETTING

The trial will initially run as a single center study in order to assess reproducibility and feasibility across different sites. The main host center will be The Royal Wolverhampton NHS Trust.

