6 PARTICIPANT ELIGIBILITY CRITERIA

6.1 Inclusion criteria

- Participant is willing and able to give informed consent for participation in the study.
- Male or Female, aged 18+ years.
- Diagnosed with histologically or radiologically diagnosed colorectal adenocarcinoma.
- Anaemic at point of diagnosis of colorectal adenocarcinoma (Defined as haemoglobin 10g/L below WHO criteria: 120g/L for males and 110g/L for females, to account for a 10% fluctuation in Hb)
- Undergoing surgery for colorectal cancer with curative intent.
- Date of planned surgery is \geq 14 days from date of planned initiation of recruitment.
- Able (in the investigators opinion) and willing to comply with all study requirements.
- Willing to allow his or her General Practitioner and consultant, if appropriate, to be notified of participation in the study.

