6.2 Exclusion criteria

- Patients with mental health issues or learning disabilities resulting in their inability to consent to the study

- Patients who do not have a histological diagnosis of colorectal adenocarcinoma
- Female participants who are pregnant, lactating or planning a pregnancy during the course of the study.
- Patients with evidence of iron overload or disturbances in utilisation of iron as stated in the product SPC.
- Previous gastric, small bowel or colorectal surgery (where ≥50% of stomach or terminal ileum has been resected)
- Chemotherapeutic treatment within the last 4 weeks.
- Known previous anaemia not attributable to colorectal carcinoma (i.e. anaemia in patients with well established, inflammatory disorders)
- Known haematological disease.
- Features necessitating urgent surgery (e.g. obstructive symptoms).
- Previous allergy to intravenous or oral iron or related iron products.
- Patients who are unable to consent.
- Any other significant disease or disorder which, in the opinion of the Investigator, may either put the participants at risk because of participation in the study, or may influence the result of the study, or the participant's ability to participate in the study.
- Participants who have participated in another research study involving an investigational product in the past 12 weeks
- Confirmed liver or lung metastases

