7.8 Withdrawal criteria

There will be intention-to-treat analyses carried out. Analysis of all participants who have been randomised will be undertaken regardless of withdrawal. The reason for withdrawal will

be recorded in the CRF. Each participant has the right to withdraw study at any time. A participant will be withdrawn from the study if any of the following occurs:

- Absence of anaemia on postoperative days 2, 3 and 5.
- Pregnancy
- Ineligibility (either arising during the study or retrospective having been inadvertently overlooked at screening)
- Significant protocol deviation as defined by the CI
- An adverse event which requires discontinuation of the study medication or results in inability to continue to comply with study procedures
- Disease progression which requires discontinuation of the study medication or results in inability to continue to comply with study procedures
- Patients who do not undergo an operation as a result of a change in fitness for surgery will be excluded.
- Consent withdrawn.
- Lost to follow up

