7.9 Collection, storage and analysis of clinical samples

All blood samples will be taken and delivered immediately for process in a CPA NHS laboratory at the individual study site. Processing of blood samples will follow the NHS laboratory protocols in keeping with Good Laboratory Practice. If consented for the optional sample sub-study, samples will be stored within the research secure repository within the trust in keeping with standard research protocols.

Please refer to the laboratory manual for details of sample collection, storage and destruction protocols.

Sampling methods include:

Faecal and blood samples will be collected at base line and days 2, 3, 5 and 12 postoperatively. Surgical resections will be collected at time of surgery.

1. Faecal samples will be collected in universal tubes 2-3 tubes per patient and put on ice until transferred to -80 freezer.
2. Serum will be prepared from the blood samples as follows:

Collect blood in a sterile 15 ml test tube or a plastic vacutainer containing no anticoagulants.

Incubate tubes in an upright position at room temperature for 30-45 minutes (no longer than 60 minutes). This will allow enough time for the blood to clot.

If using vacutainers with clot activators such as the BD Vacutainer Plus Plastic Serum Tube (red top), invert carefully 5 times before incubation.

Centrifuge tubes at 1500 x g for 10 minutes with the break OFF.

Use Pasteur pipette to carefully transfer equal amount of the supernatant into two cryotubes without disturbing the cloudy cell layer below the supernatant (10 ml of whole blood produces 4-6 ml of serum).

Immediately store tubes in -80 freezer.

Serum samples will be tested for chemokines and inflammatory markers by Multiplex immune assays.

3. Surgical resections will be collected in 2ml tubes on ice (preferably liquid nitrogen or dry ice) and immediately frozen in -80 freezer.

Tissue resections will be used to determine the expression of immune cells and their activation markers as well as proliferation and apoptotic markers using immunofluorescence microscopy. Resections will also be used to study the microbiome using 16s-rRNA gene sequencing and taxonomic analysis to determine changes in probiotic and pathogenic bacterial populations.

4. Paraffin embedded sections will be collected from the pathology archives at a later date.

Paraffin embedded sections may also be used to determine the expression of inflammatory markers using immunohistochemistry.

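### Retention has no stated denominator, and withdrawals that the protocol itself requires are not separated from non-concordance

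*Combined protocol and SAP*

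**What the plan says.** Section 3.1 introduces the primary measures with "Feasibility measures will include" and names four: eligible patients, exclusion, acceptability of recruitment and retention. Section 3.3.1 sets no criteria in advance. Section 10.2 uses the data to help size a larger study and predict how long recruitment would take.

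Section 10.3.2 expands the list to include "withdrawal of patients (non-concordance), compliance with the randomised treatment, study retention (retention rates". It also lists exclusion, glossed as screen failure. It does not say who forms the denominator for retention.

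Section 7.8 commits to analysing everyone randomised, whether or not they withdraw. It then lists grounds on which a participant will be withdrawn. Among them are absence of postoperative anaemia, an operation that does not go ahead because fitness has changed (here the word used is excluded), and "Ineligibility (either arising during the study or retrospective having been inadvertently overlooked at screening". Reasons are recorded in the CRF. Section 10.5 excludes from the trial a participant whose missing data cannot be recovered or resampled.

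On diagnosis, 6.1 includes patients "Diagnosed with histologically or radiologically diagnosed colorectal adenocarcinoma", while 6.2 excludes "Patients who do not have a histological diagnosis of colorectal adenocarcinoma".

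On setting, section 4 states "This study will be a single centre, open labelled, randomised controlled trial". Section 5 states "The trial will initially run as a single center study in order to assess reproducibility and feasibility across different sites". Section 7.9 has samples "delivered immediately for process in a CPA NHS laboratory at the individual study site", and sections 8.4 and 13.2 also use wording that implies more than one site.

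**The concern.** In a feasibility trial with no progression criteria, the reported rates are the main product. A rate needs a fixed numerator and denominator. Here, a patient who is randomised, recovers without anaemia and is removed under the protocol's own rule could be counted in three ways: as a non-concordant withdrawal (the gloss in 10.3.2), as a screen failure (7.7 speaks of such patients completing screening), or as a loss from an all-randomised retention rate. These readings say different things about whether a larger trial is feasible. Non-concordance suggests that patients will not stay with the treatment, whereas removal for lack of anaemia says only that the entry test comes after randomisation.

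The number of such patients, and who counts as randomised, also depend on rules that differ between sections. If two teams applied the same plan to the same patients, they could report different primary results and carry different drop-out allowances into the next trial.

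**Working it through.** **The plan's own figure.** Section 10.1 gives 20 per arm, and 2 × 20 = 40, which agrees. No retention or withdrawal rate is stated, so there is nothing further to reproduce.

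**The sections side by side**

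- *Withdrawal trigger.* 7.8 joins days 2, 3 and 5 with *and*. The pathway-entry paragraph of 7.7 joins them with *or*, yet the same paragraph keeps a patient who is not anaemic on day 2 in the study and allows entry on day 3 or day 5. Section 4 uses *either … or* and can be read both ways. Section 8.5 starts treatment once anaemia is confirmed on any of the three days.
- *Early discharge.* 7.7 takes day 5 blood only from inpatients. A non-anaemic patient discharged before day 5 cannot meet the *and* wording as written, and no section says what happens to that patient.
- *Randomisation time.* Section 4: before the operation. Appendix 1: the day-of-surgery visit. Section 7.3: participants learn their allocation after the operation. Section 7.7: randomised after the operation.
- *Denominator.* 7.8 analyses all randomised. The line in 7.8 on operations not performed and the missing-data rule in 10.5 each take patients out. The all-randomised sentence concerns the intention-to-treat analyses and is not tied to retention.

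**Size, on assumed rates.** Inputs:

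- N = 40 randomised (section 10.1).
- w = proportion withdrawn as non-anaemic = 10%. This is an assumption, taken from the Background's figure of up to 90% anaemic after surgery without intervention.
- r = proportion followed up among the rest = 85% (assumption).
- Withdrawn patients have no 8–12 week visit (assumption).

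Steps:

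1. Withdrawn by rule: 0.10 × 40 = 4. Pathway entrants: 40 − 4 = 36.
2. Followed up: 0.85 × 36 = 30.6, rounded to 31.
3. Retention on entrants: 31/36 = 86.1% (Wilson 95% CI 71.3 to 93.9).
4. Retention on all randomised: 31/40 = 77.5% (62.5 to 87.7).
5. Gap: w × (31/36) = 0.10 × 0.861 = 8.6 percentage points. Both rates come from the same 31 patients, so the gap is one of definition and not of sampling, although the intervals overlap.
6. Losses: 40 − 31 = 9, of which 4 are required by the protocol. If the other 36 − 31 = 5 are all classed as withdrawals, non-concordance is 9/40 = 22.5% with the required withdrawals in and 5/40 = 12.5% with them out.
7. As a drop-out allowance: 1/0.861 = 1.16 per pathway entrant and 1/0.775 = 1.29 per patient randomised, a ratio of 40/36 = 1.11. Each is right for its own question. The risk is in using one for the other.

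**Range.** With w = 0 the two rates coincide. With w = 10% and no other loss they are 36/36 = 100% and 36/40 = 90%. An upper case of w = 25% uses the Background's 75% still anaemic at operation after intravenous iron. It gives 0.85 × 30 = 25.5, rounded to 26: 26/30 = 86.7% (70.3 to 94.7) against 26/40 = 65.0% (49.5 to 77.9). That 75% is a preoperative figure, so 25% is probably too high for the days after surgery.

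**The case against.** The case for leaving the plan alone is that intent can mostly be inferred, and several stronger readings do fail.

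- *A reader might infer that required withdrawals are certain to be reported as non-concordant.* The documents do not establish that. The gloss in 10.3.2 is a parenthesis and not a counting rule, and 7.7 leaves the screen-failure route open. What stands is that the plan does not choose.
- *A reader might take the* or *in 7.7 literally and expect many more withdrawals.* Sections 4, 7.7 and 8.5 make that unworkable, because a patient normal on day 2 would be gone before the later entry that those sections allow. The text suggests that absence of anaemia on all tests is meant. The wording conflict and the early-discharge gap remain.
- *A reader might infer that the time of randomisation is wholly open.* Section 4, Appendix 1 and 7.3 together favour randomisation before the operation with disclosure afterwards, which leaves 7.7 as the outlier. On that reading, the all-randomised count is affected only by operations cancelled between randomisation and surgery.
- *A reader might put a number on radiology-only patients.* The documents give no share. Read together, 6.1 and 6.2 already require histology, so the radiological option has no effect. The practical risk is a patient enrolled from one list and later withdrawn as ineligible.
- *The setting.* No listed measure is cross-site, section 5 says the single-centre phase is initial, and 3.1 looks ahead to a later multi-centre trial. This is a conflict of stated aim and does not damage an endpoint.

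It is also fair that withdrawal reasons are recorded, so either denominator can be rebuilt from the data. That makes the repair cheap, but it does not supply the definition.

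**Conclusion.** The point holds. Retention, one of the four primary measures in 3.1, has no stated denominator. Withdrawals required by 7.8 can be classed as non-concordance or as screen failure. The rules that set their number and the all-randomised count conflict between sections 4, 7.7, 7.8 and 10.5. On the assumed 10% withdrawn and 85% followed up, the choice of denominator moves retention from 86% to 78%, about 9 points. The gap is nil if nobody is withdrawn and about 22 points in the upper case. These figures show scale only: the anaemia rates are background values from other settings and the follow-up rate is assumed.

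A reader might go further and conclude that the feasibility results will be unusable. The documents do not support that, since the recorded reasons allow both rates to be recovered. The conflicts on diagnosis and setting are real but minor. The plan should be changed before the feasibility rates are reported.

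**What to change.** 1. Reconcile sections 4, 7.7 and 7.8 on when absence of postoperative anaemia leads to withdrawal, including for patients discharged before day 5. Reconcile 7.7 with section 4, 7.3 and Appendix 1 on when randomisation takes place. The sponsor decides both.
2. In 10.3.2, report retention to the 8–12 week visit on all randomised and, separately, on patients who entered their allocated pathway. List every loss between randomisation and pathway entry by reason, and do not count withdrawals that the protocol requires as non-concordance.
3. Align 10.5 and the line in 7.8 on operations not performed, so that these patients, once randomised, stay in the all-randomised denominator.
4. Make 6.1 and 6.2 state one diagnostic requirement, chosen by the sponsor.
5. Either limit section 5 to feasibility at one centre or state in section 4 that further sites are intended, and bring the site wording in 7.9, 8.4 and 13.2 into line.

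The cost is protocol wording and a second retention figure. No visits or data items are added, because 7.8 already records the reason for withdrawal.

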10.3.3 Secondary outcome analysis

Outcomes for the secondary objectives include evaluation of transfusion rates, change in blood indices and change, quality of life. The median change in transfusion rates and haemoglobin will be reported. Quality of life will be reported as change from baseline and assessed for minimal clinically important difference.

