3.2 Secondary objectives

- To investigate whether the use of ferric maltol could improve the postoperative quality of life of patients after colorectal cancer surgery compared to standard care.

- To calculate the change in postoperative haemoglobin and haematinics in response to ferric maltol compared to standard care.
- To compare postoperative allogenic red blood cell transfusion rates in patients receiving ferric maltol or standard care
- To review the tolerability of ferric maltol for the treatment of postoperative colorectal cancer patients
- To compare length of stay and complication rates in patients receiving ferric maltol or standard care postoperatively.
- To assess for immunological and metabolomic peri-operative differences between patients receiving ferric maltol preparations and standard care.

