3.3.2 Secondary endpoints/outcomes

1. Levels of haemoglobin and haematinic markers (full blood count, ferritin, iron, transferrin, and transferrin saturation). Immunological and metabolomic markers will also be assessed. These will be measured at a point preoperatively before intravenous iron treatment, on the day of surgery and at defined time points postoperatively during the administration of oral ferric maltol or during standard care
2. Side-effects and reactions to ferric maltol administration
3. Peri- and post-operative morbidity and mortality
4. Post-operative complications

5. Post-operative length of stay
6. Post-operative allogenic blood transfusion.
7. Quality of life as determined by the SF36, EQ-5D and FACT-An questionnaires.

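### The transfusion summary in Section 10.3.3 (a median change in rates) does not fit a post-operative transfusion endpoint, and the haemoglobin change has no named reference time

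*Combined protocol and SAP*

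**What the plan says.** All references are to the combined protocol and SAP.

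**Transfusion.** The objective in Section 3.2 is "To compare postoperative allogenic red blood cell transfusion rates in patients receiving ferric maltol or standard care". The endpoint in Section 3.3.2 is "Post-operative allogenic blood transfusion", with no unit of measure. The only analysis sentence specific to transfusion, in Section 10.3.3, is "The median change in transfusion rates and haemoglobin will be reported". Section 10.2 gives the general rule: "Numbers and percentages will be presented for categorical data, mean and standard deviations for normally distributed continuous data", with median and inter-quartile range for skewed data.

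Section 7.7 has transfusion recorded at three points: pre-operative transfusion on the morning of surgery, peri-operative transfusion at day 2, and post-operative transfusion at the outpatient visit. Under Section 8.5, ferric maltol starts only after anaemia is confirmed on the day 2, 3 or 5 sample.

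**Haemoglobin.** The objective in Section 3.2 is "To calculate the change in postoperative haemoglobin and haematinics in response to ferric maltol compared to standard care". On timing, Section 3.3.2 says of the blood markers: "These will be measured at a point preoperatively before intravenous iron treatment, on the day of surgery and at defined time points postoperatively". Section 7.7 and Appendix 1 schedule samples at the baseline (consent) visit, on the day of surgery, on days 2, 3 and 5, and at follow-up. Section 10.3.3 ties quality of life to baseline but names no reference for haemoglobin.

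**Use of the data.** Section 10.2 says that "data will also be used to help determine an adequate sample size for a larger study"; Section 3.3.1 says the same of the sample size and outcome measures of a definitive trial.

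**The concern.** The sentence in Section 10.3.3 names a statistic that does not match the endpoint. If a transfusion rate is the proportion of patients transfused, each arm has one figure and there is nothing to take a median of. If it is units per patient, the median exists but is insensitive when fewer than half of an arm are transfused. In either case a change needs a starting value, and none is defined; pre-operative transfusion is recorded but never named as the reference.

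For haemoglobin, two analysts could follow the plan and report different changes from the same data. A change from the consent visit includes the response to intravenous iron and the operative blood loss. A change from the day of surgery includes the blood loss only. A change from a post-operative value includes neither. Section 10.3.3 also fixes a median, whereas Section 10.2 would give mean and SD if the data are normal.

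What is at stake is the value of these summaries as inputs to the definitive trial: an event proportion for transfusion, and a well-defined SD for haemoglobin.

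**Working it through.** **Inputs.** 20 patients per arm (Section 10.1). The documents give no transfusion rate, haemoglobin SD, correlation or dropout figure, so everything below that needs one uses assumed values. The plan has no figure of its own to reproduce here.

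**1. When is the median number of units 0?** With 20 patients the median is the average of the 10th and 11th ordered values. Both are 0 if at most 9 patients are transfused. With transfusion risk p, P(median = 0) = P(X ≤ 9), X ~ Binomial(20, p). If both arms share the same p, the probability for both is the square.

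| Assumed p | One arm of 20 | Both arms |
|---|---|---|
| 10% | >0.999 | >0.999 |
| 20% | 0.997 | 0.995 |
| 30% | 0.952 | 0.91 |
| 40% | 0.755 | 0.57 |

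With 15 per arm after losses (assumed), the condition is X ≤ 7 and the one-arm figures are >0.999, 0.996, 0.950 and 0.787.

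**2. Does the inter-quartile range in Section 10.2 help?** With 20 patients the upper quartile lies around the 15th and 16th ordered values.

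- 8/20 versus 2/20: both medians are 0. In the first arm 12 values are 0, so the upper quartile is at least 1 unit; in the second, 18 values are 0, so it is 0. The range separates the arms. Risk difference 0.40 − 0.10 = 30 points, Newcombe 95% CI 3 to 53.
- 4/20 versus 1/20: 16 and 19 values are 0, so both medians and both upper quartiles are 0. Risk difference 0.20 − 0.05 = 15 points, 95% CI −7 to 37.

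So median with inter-quartile range shows a difference in the first case and none in the second. Number and percentage shows it in both.

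**3. Counting window.** Suppose a share s of the counted transfusions is given before treatment can start, and treatment halves the later ones. The overall reduction is 0.5 × (1 − s): 37.5, 25 and 12.5% for s = 0.25, 0.50 and 0.75 (all assumed). Counting every post-operative transfusion is a valid comparison under randomisation, but the effect is diluted. The end of the window is not fixed either: follow-up ends at 8–12 weeks after surgery (Section 7.7, Appendix 1), treatment runs to 12 weeks after the operation (Section 4), and Section 1 has follow-up to about 12 weeks after discharge. These passages must be reconciled.

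**4. What adjustment for the haemoglobin reference would add.** Let the final value have SD 1, the reference SD k, and their correlation be r. The variance of the change-score difference divided by that of the adjusted difference is (1 + k² − 2kr)/(1 − r²).

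| Assumed r | k = 1 | k = 0.7 |
|---|---|---|
| 0.3 | 1.54 | 1.18 |
| 0.5 | 1.33 | 1.05 |
| 0.7 | 1.18 | 1.00 |

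The largest gain shown is 1 − 1/1.54 = 0.35, about one third of the variance; the smallest is none. The residual SD would still be imprecise: with n − 3 degrees of freedom its 95% CI is 0.82 to 1.29 times the estimate with all 40 analysed, and 0.79 to 1.36 times with 30 (assumed).

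**The case against.** The strongest reply is that Section 10.2 already covers this. Transfused or not is categorical, so number and percentage is called for; units per patient is skewed, so the median comes with an inter-quartile range, which separates the arms at 8/20 versus 2/20. This largely stands. A reader might infer that the plan as written would hide any transfusion difference, and the documents do not support that. What remains is that the one sentence specific to transfusion names a different statistic, and nothing says which sentence governs.

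A second reply is that the wording is loose rather than wrong. Section 10.2 speaks of change being presented between the two groups, so a change in transfusion rates may mean a between-arm difference, as in the objective. That is a fair reading, and it removes the missing pre-operative reference; the word median still does not fit it.

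Third, the window is not wholly absent. The endpoint is post-operative, and pre-operative transfusion is recorded separately. What is open is whether the day 2 peri-operative record counts, and the end date.

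Fourth, a reader might infer that quality of life also lacks a reference. It does not: Section 10.3.3 names baseline, Section 7.5 includes the questionnaires in the baseline data, and Appendix 1 labels that visit.

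Last, unadjusted change is valid under randomisation, so the absence of adjustment is not an error. That stands in full; the adjusted difference below is offered only as an addition.

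**Conclusion.** The point holds as a minor one. The transfusion sentence in Section 10.3.3 does not fit its endpoint: as a proportion the statistic does not exist, and as units per patient it is 0 with probability 0.952 per arm at an assumed 30% transfused and 0.755 at 40%. The general rule in Section 10.2 limits the damage, so the aim is to stop the specific sentence from overriding number and percentage. The status of transfusions given before treatment can start is open; including them is valid but may dilute an effect. The haemoglobin reference time is not named, and the fixed median departs from Section 10.2.

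The probabilities rest on assumed transfusion rates, the dilution figures on assumed shares, and the gain from adjustment on assumed correlations; that gain may be small or nil. These are descriptive secondary outcomes in a feasibility trial of 40, and the primary feasibility endpoint is unaffected. A stronger inference, that the trial's main conclusion or the validity of its comparisons is at risk, has no support in the documents.

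**What to change.** 1. **Transfusion, Section 10.3.3.** Replace the transfusion part of the sentence with wording such as: the number and percentage of patients given an allogenic red cell transfusion after surgery will be reported per arm, with the risk difference and 95% CI; units transfused will be given as a supplement. State the start and end of the counting window, and show transfusions before and after entry to the treatment pathway separately.

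2. **Haemoglobin, Section 10.3.3.** Name one pre-treatment reference, chosen from the consent visit, the day of surgery, or the post-operative value before treatment starts. Summarise the change by the rule in Section 10.2 (mean and SD, or median and inter-quartile range). Alongside these summaries, report the between-arm difference in final haemoglobin adjusted for that reference, with 95% CI, residual SD, number analysed, and the correlation between reference and final value. The residual SD and the correlation are inputs for sizing the definitive trial.

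Cost: a few sentences in the plan and a few lines of analysis. The haemoglobin and transfusion data are already collected, and the computer record of transfusions is already a source document (Section 11.1). No new visit or sample is needed.
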